**Table 14: Analysis Windows for PK Concentration**

Visit	Scheduled Day	Lower Bound	Upper Bound
Week 4	29	2	49
Week 12	85	50	126
Week 24	169	127	>210
Week 36	253	211	>211

**Table 15: Analysis Windows for Clinical Safety Laboratory Measurements**

Visit	Scheduled Day	Lower Bound	Upper Bound
Screening	<1	<1	<1
Day 1	1	1	1
Week 2	15	2	21
Week 4	29	22	42
Week 8	57	43	70
Week 12	85	71	98
Week 16	113	99	126
Week 20	141	127	154
Week 24	169	155	175
Week 26	183	176	189
Week 28	197	190	210
Week 32	225	211	238
Week 36	253	239	266
Week 40	281	267	294
Week 44	309	295	322
Week 48	337	323	350
Follow-up	365	351	>351

## 12.4. Mspline Value for Calculation of Predicted FVC

**Table 16: Mspline Value**

Age (yrs)	Male	Female	Age (yrs)	Male	Female
18	0.147849088	0.135507529	50	-0.006647706	0.028303776
19	0.160315109	0.140628299	51	-0.014542406	0.020206649
20	0.167159394	0.143647414	52	-0.022604908	0.011905392
21	0.169722148	0.145330204	53	-0.030845244	0.00339698
22	0.16923214	0.146039097	54	-0.039274925	-0.005323975
23	0.166543254	0.145870185	55	-0.04790158	-0.014258162
24	0.162315681	0.144942845	56	-0.056735557	-0.023411261
25	0.157092735	0.143626724	57	-0.065782826	-0.032797239
26	0.151293448	0.142211366	58	-0.07504859	-0.042417299
27	0.145106883	0.140771596	59	-0.084531216	-0.052260185
28	0.138681964	0.13919976	60	-0.094214527	-0.062313185
29	0.132266867	0.137441293	61	-0.104078877	-0.072556666
30	0.125876212	0.135494281	62	-0.114093666	-0.082975133
31	0.119459845	0.133330256	63	-0.124218952	-0.093558031
32	0.113049003	0.130878076	64	-0.134413719	-0.104301259
33	0.106735805	0.12804587	65	-0.14465155	-0.115203896
34	0.100550635	0.124811373	66	-0.154914171	-0.126261624
35	0.094499318	0.121203564	67	-0.165181495	-0.137466925
36	0.088531508	0.117238065	68	-0.175439763	-0.148808471
37	0.082567889	0.112889589	69	-0.185681902	-0.160268368
38	0.076537303	0.108171834	70	-0.195901978	-0.171827557
39	0.070402479	0.103107309	71	-0.20609542	-0.183468534
40	0.064129074	0.097699941	72	-0.216260542	-0.195173143
41	0.057677943	0.091939589	73	-0.226393699	-0.206921242
42	0.051046568	0.085825419	74	-0.236485333	-0.218692812
43	0.04427255	0.079389589	75	-0.246523325	-0.230468005
44	0.037387387	0.07268763	76	-0.256496316	-0.242227571
45	0.030394993	0.06577409	77	-0.266395583	-0.253951742
46	0.023277783	0.058677615	78	-0.276212134	-0.265621352
47	0.01602077	0.051384134	79	-0.285939277	-0.277219902
48	0.008623361	0.043889005	80	-0.295573257	-0.288731661
49	0.001072775	0.036196648			

## 12.5. Sample SAS Codes

The followings are the prototype of the SAS codes that will be used for the analysis. The final version of the statistical programming codes to be used will be determined prior to the database lock.

### 1. MMRM for the primary endpoint

```
proc mixed data = artot method = reml;  
  class <usubjid> <visit> <treatment> <baseline riluzole use> <baseline edaravone use>;  
  model <change in ALSFRS-R total score> = <visit> <treatment> <baseline ALSFRS-R total score>  
    <baseline riluzole use> <baseline edaravone use> <visit>*<treatment>  
    <visit>*<baseline ALSFRS-R total score>/ddfm=kr;  
  repeated <visit> / subject = <usubjid> type = un;  
  lsmeans <visit>*<treatment> / pdiff cl;  
run;
```

Note: If the 2nd interim analysis result leads to an increase of the sample size, the final analyses will include the status of being included or excluded from the 2nd interim analysis as a covariate in the model.

### 2. Multiple imputation within each treatment group under MAR assumption

```
proc mi data=datain minimum=0 maximum=48 round=1 nimpute=50 out=dataout;  
  class <baseline riluzole use> <baseline edaravone use>;  
  fcs reg(<Week 4 ALSFRS-R total score> = <baseline riluzole use> <baseline edaravone use>);  
  fcs reg(<Week 8 ALSFRS-R total score> = <baseline riluzole use> <baseline edaravone use>  
    <Week 4 ALSFRS-R total score>);  
  fcs reg(<Week 12 ALSFRS-R total score> = <baseline riluzole use> <baseline edaravone use>  
    <Week 4 ALSFRS-R total score> <Week 8 ALSFRS-R total score>);  
  fcs reg(<Week 16 ALSFRS-R total score> = <baseline riluzole use> <baseline edaravone use>  
    <Week 4 ALSFRS-R total score> <Week 8 ALSFRS-R total score>  
    <Week 12 ALSFRS-R total score>);  
  fcs reg(<Week 20 ALSFRS-R total score> = <baseline riluzole use> <baseline edaravone use>  
    <Week 4 ALSFRS-R total score> <Week 8 ALSFRS-R total score>
```

```
                                <Week 12 ALSFRS-R total score> <Week 16 ALSFRS-R total score>);  
fcs reg(<Week 24 ALSFRS-R total score> = <baseline riluzole use> <baseline edaravone use>  
                                <Week 4 ALSFRS-R total score> <Week 8 ALSFRS-R total score>  
                                <Week 12 ALSFRS-R total score> <Week 16 ALSFRS-R total score>  
                                <Week 20 ALSFRS-R total score>);
```

```
var <baseline riluzole use> <baseline edaravone use> <Week 4 ALSFRS-R total score> <Week 8 ALSFRS-R total score>  
<Week 12 ALSFRS-R total score> <Week 16 ALSFRS-R total score> <Week 20 ALSFRS-R total score>  
<Week 24 ALSFRS-R total score>;
```

run;

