## **6.4. Data Presentation Conventions**

The following conventions will be applied to data presentations:

- For continuous variables, mean and median values are formatted to one more decimal place than the measured value. Standard deviation values are formatted to two more decimal places than the measured value. Minimum and maximum values are presented with the same number of decimal places as the measured value.
- For categorical variables, the count and percentage of responses are presented in the form XX (XX.X%).
- Date variables are formatted as DDMMYYYY for presentation. Time is formatted from 0:00 to 23:59 as HH:MM for presentation.
- P-values, if applicable, will be presented to 4 decimal places. If the p-value is less than 0.0001 then it will be presented as <0.0001. If the rounded result is a value of 1.000, it will be displayed as >0.9999.
- Unless otherwise stated, any statistical tests performed following the second interim analysis (which will be performed at a significance level of 0.0001) will use 2-sided tests at the 0.0499 significance level.

The table and listing shells and table of contents as part of this SAP provide the expected layout and titles of the tables, listings and figures. Any changes to format, layout, titles, numbering, or any other minor deviation will not necessitate a revision to the SAP nor will it be considered a deviation from planned analyses. Only differences in the analysis methods or data handling will require such documentation. The appropriate listings supporting the tables will be included and are not specified in the individual sections throughout the document.

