## 8.5. Multiple Comparisons and Multiplicity

The null hypothesis for the primary and secondary efficacy endpoints will be tested in a prespecified order using a closed testing procedure. This procedure will maintain the family-wise error rate at two-sided significance level of 0.0499 for all primary and secondary hypotheses tested in a confirmatory sense. The testing steps are described as follows:

- Step 1: The null hypothesis for the primary endpoint  $H_{01}$  is that there is no treatment difference in the change from baseline to Week 24 in ALSFRS-R total score between patients randomized to placebo and those randomized to reldesemtiv in the FAS. The hypothesis will be tested at the two-sided significance level of 0.0499. If this hypothesis is rejected, testing will proceed to Step 2; otherwise testing will stop.
- Step 2: The null hypotheses for the first secondary endpoint  $H_{02}$  is that the Mann-Whitney probability of a more favorable status in reldesemtiv or placebo group in the FAS is 0.5. The status is quantified by joint ranks based on the combined assessment of change in ALSFRS-R total score, time to onset of respiratory insufficiency, and survival time up to Week 24. The hypotheses will be tested at the two-sided significance level of 0.05. If this hypothesis is rejected, testing will proceed to Step 3; otherwise testing will stop.
- Step 3: The null hypotheses  $H_{03}$  is that there is no treatment difference in change from baseline to Week 24 in the percent predicted FVC between patients randomized to placebo and those randomized to reldesemtiv in the FAS. The hypotheses will be tested at the two-sided significance level of 0.05. If this hypothesis is rejected, testing will proceed to Step 4; otherwise testing will stop.
- Step 4: The null hypotheses  $H_{04}$  is that there is no treatment difference in change from baseline to Week 24 in the ALSAQ-40 total score between patients randomized to placebo and those randomized to reldesemtiv in the FAS. The hypotheses will be tested at the two-sided significance level of 0.05. If this hypothesis is rejected, testing will proceed to Step 5; otherwise testing will stop.

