## 8.6. Analysis of the Primary Efficacy Endpoint

### 8.6.1. Primary Efficacy Analysis

The primary efficacy endpoint of the trial is the change from baseline to Week 24 in ALSFRS-R total score. The estimand of the primary efficacy endpoint is the difference in the mean changes from baseline to Week 24 in ALSFRS-R total score between patients randomized to placebo and those randomized to reldesemtiv in the FAS.

The analysis for the primary efficacy endpoint will be conducted using a mixed model for repeated measures (MMRM) based on a restricted maximum likelihood method (SAS® PROC MIXED default). The model terms will include treatment group, baseline ALSFRS-R total score, visit, riluzole use at baseline, edaravone use at baseline as well as baseline-by-visit and treatment group-by-visit interactions. In addition, other baseline covariates identified by stepwise selection in a regression model will also be included in the model if they are key predictor variables for the change from baseline to Week 24 in ALSFRS-R total score. The regression model used to identify baseline covariates will include change from baseline to Week 24 in ALSFRS-R total score as response variable and pre-study disease progression rate, age and baseline percent predicted FVC as model terms. The stepwise selection process with significance at 0.25 level for a variable to be entered to the model and with significance at 0.1 level for a variable to remain in the model will be used. The best-fit model according to AIC will be selected. The evaluation will be performed based on the blinded data before the database lock. An unstructured variance-covariance matrix will be used for the model. Observed data collected up to Week 24 in the FAS will be included in the model.

Prior to applying the MMRM, multiple imputation with fifty invocations under the MAR paradigm will be performed to impute missing data (see [Section 8.6.1.1](#) for imputation method).

Least squares mean (LSM), LSM difference and the corresponding standard error, 95% CI and p-value will be presented. The components used to derive main estimator of the primary analysis are shown in [Table 4](#).

Sensitivity analyses will be conducted to support the robustness of conclusions based on the primary analysis results. See [Section 8.6.2](#) for sensitivity analyses.

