### **8.6.1.1. Imputation of the Missing Data for the Primary Efficacy Analysis**

The extent of missing data and the pattern of missing data reasons will be tabulated. Missing ALSFRS-R total score will be imputed for the primary efficacy analysis described in [Section 8.6.1](#). For each randomized treatment group, the missing data will be filled sequentially starting at the earliest time point and progressing until the last time point based on a multivariate joint normal imputation model ([Schafer 1997](#)). The imputation model will include the following terms: ALSFRS-R total score at previous visits including baseline (in reldesemtiv or placebo group), riluzole use and/or edaravone use at baseline, and other covariates selected using stepwise regression for the primary analysis (see [Section 8.6.1](#)) such as pre-study disease progression rate, age and/or baseline percent predicted FVC. Fifty set of complete data will be generated for analysis to produce 50 sets of estimates. Rubin's imputation rules ([Rubin 1987](#)) will be used to combine the LSM estimates of the treatment difference, 95% confidence interval and p-value. The example SAS code can be found in [Section 12.5](#).

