### 3. Multiple imputation for missing values in the reldesemtiv group with placebo distribution

Missing data in the reldesemtiv group will be combined with all data in the placebo group for imputation, and will be filled sequentially starting at the earliest time point and progressing until the last time point. Below is an example of filling missing data at Week 8 for the reldesemtiv group using placebo data.

```
data imp; set pbo act_mis(where=(Wk8=));  
proc mi data=imp seed=&seed out=miout NIMPUTE=50;  
  mcmc IMPUTE=FULL;  
  var Wk4 Wk8;  
run;
```

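### With 50 imputations and no recorded seed, a primary p-value near 0.05 carries avoidable Monte Carlo noise (SD about 0.004 to 0.009); about 1000 imputations would largely remove it

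*SAP*

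**What the plan says.** SAP 8.6.1 states that, before the MMRM is fitted, "multiple imputation with fifty invocations under the MAR paradigm will be performed to impute missing data". SAP 8.6.1.1 repeats the number, "Fifty set of complete data will be generated for analysis to produce 50 sets of estimates", calls for pooling by Rubin's rules, and refers to 12.5 for the code.

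In 12.5, item 2 (imputation within arm under MAR) opens with "proc mi data=datain minimum=0 maximum=48 round=1 nimpute=50 out=dataout". Item 4 (tipping point) uses the same statement. Neither has a seed option. Item 3 (placebo-based imputation, a sensitivity analysis) does: "proc mi data=imp seed=&seed out=miout NIMPUTE=50". There the seed is a macro variable whose value is not given anywhere. SAP 12.5 introduces all of this as prototype code: "The final version of the statistical programming codes to be used will be determined prior to the database lock".

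On the primary test, SAP 8.5 Step 1 says: "The hypothesis will be tested at the two-sided significance level of 0.0499". Steps 2 to 5 open only if Step 1 rejects. SAP 6.4 reports p-values to four decimals. SAP 8.7.1.1 sends the first secondary endpoint back to the 8.6.1.1 imputation, so the number 50 carries over to it. Neither document sets a limit on Monte Carlo error or commits to reporting it.

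**The concern.** Multiple imputation draws random values, so the pooled estimate, confidence interval and p-value depend partly on the random stream. Nothing in the plan fixes that stream for the primary analysis, and 50 datasets may leave visible noise in a p-value that is compared with a sharp cut-off. If the result is close, the primary verdict and access to the four secondary tests could turn on which run was made, and the reported figure could not be reproduced exactly from the locked data and the SAP alone.

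**Working it through.** **Plan's own figure.** Inputs from SAP 4.3.1: difference 1.8, SD 5.5, two-sided 0.05, 90% power, 2:1 allocation. Placebo n = (1.960 + 1.282)² × 5.5² × (1 + 1/2) / 1.8² ≈ 147.2, rounded up to 148. The total is 148 + 296 = 444, and 444 / 0.80 = 555. Both stated numbers are reproduced, with an implied 20% loss. The expected test statistic at the design effect is 1.8 / [5.5 × √(1/296 + 1/148)] = 1.8 / 0.554 = 3.25.

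**Noise in the p-value.** With m imputations,

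SD(z) ≈ √[ FMI/m + (1.96 × 0.5 × FMI)² × 2/(m − 1) ], and near p = 0.05, SD(p) ≈ 2φ(1.96) × SD(z) = 0.117 × SD(z).

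Example with FMI 0.10 and m = 50: √(0.00200 + 0.00039) = 0.0489, so SD(p) = 0.0057.

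FMI is an assumption, because the documents give none.

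| FMI | SD(p), m = 50 | 95% half-width, m = 50 | SD(p), m = 1000 | 95% half-width, m = 1000 |
|---|---|---|---|---|
| 0.05 | 0.0039 | 0.008 | 0.0009 | 0.0017 |
| 0.08 | 0.0050 | 0.010 | 0.0011 | 0.0022 |
| 0.10 | 0.0057 | 0.011 | 0.0013 | 0.0025 |
| 0.15 | 0.0073 | 0.014 | 0.0016 | 0.0032 |
| 0.20 | 0.0087 | 0.017 | 0.0019 | 0.0038 |

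**Simulation check.** The set-up was 555 patients at 2:1 and six visits, with sequential regression imputation by arm (bounded 0 to 48, rounded), m = 50, and Rubin's rules. A Week 24 ANCOVA stood in for the MMRM. Each dataset was re-imputed 100 times.

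- 20% missing, correlated visits, p near 0.05: FMI 0.07 to 0.12 and SD(p) 0.005 to 0.007. The central 95% of re-runs ran from 0.042–0.059 (narrowest) to 0.036–0.064 (widest). Between 42% and 53% of re-runs fell at or below 0.0499.
- 10% missing: FMI 0.053, SD(p) 0.0039, central 95% 0.043–0.059.
- Extreme cases (all dropout early, or uncorrelated visits): FMI 0.18 to 0.22, SD(p) 0.009 to 0.010.
- Away from the threshold (20% missing): SD(p) 0.0017 at p = 0.01 and 0.0004 at p = 0.002. Every re-run was significant.

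**How often the verdict would change.** The chance that two independent runs fall on opposite sides of the critical value 1.961 is about SD(z) × (2/√π) × φ(1.961 − expected z). With SD(z) = 0.05:

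- Design effect, 1.8 points: 0.05 × 1.128 × φ(−1.29) = 0.05 × 1.128 × 0.174 = 0.0098, about 1%.
- True difference 1.1 points, expected z = 1.1 / 0.554 = 1.99: 0.05 × 1.128 × 0.399 = 0.0225, about 2%.

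**The case against.** The strongest reply is that the seed is a programming detail. SAP 12.5 describes its code as a prototype to be settled before database lock, and item 3 shows that seeding is already in the programmers' practice. That stands: taken alone, the missing seed is unfinished detail. It does not cover the number of imputations, which the SAP body fixes in two places. A seed makes a result reproducible but does not shrink the noise.

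A second reply is that Sensitivity Estimator 1 (SAP Table 5) fits the same MMRM without imputation and so has no Monte Carlo error. It would be a useful companion to a borderline result, but it does not decide Step 1.

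Third, 20% is the allowance for non-completers, not a forecast of missing Week 24 scores. Protocol 7.2.1 encourages patients off drug to stay in the trial, and Protocol 8 allows the ALSFRS-R by phone or video. Missingness may be lower, and the lower end of the range above would then apply.

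Some stronger readings are tempting but not supported:

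- A reader might infer that the primary p-value moves by about 0.01 whatever its value. That holds only near 0.05.
- A reader might set the noise against the 0.0001 of alpha spent at the interim and conclude that error control is broken. Alpha is a long-run error rate, and Rubin's variance already includes the finite-m term. That term widens the standard error by about FMI/(2m), for example 0.10/100 = 0.1%. A single planned run does not inflate type I error.
- A reader might infer that an unseeded run will be made after unblinding and chosen among several. The SAP says the code is settled before lock, and Protocol 6.3 keeps sites and patients blinded until the database is locked. Nothing in either document suggests selecting among runs.
- A reader might take the chance of landing within two Monte Carlo SDs of the threshold as the chance of a changed verdict. With SD(z) = 0.05 that band is 0.2 wide, giving 0.2 × 0.174 = 3.5% at the design effect and 0.2 × 0.399 = 8% at 1.1 points. Actual disagreement between two runs is about 1% and 2%.

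**Conclusion.** The point holds as a cheap improvement to the plan, not as a flaw in error control. At m = 50 a primary p-value near 0.05 has a Monte Carlo SD of about 0.004 to 0.009 for an assumed FMI of 0.05 to 0.20. In the few trials that end close to 0.0499, the random run could decide Step 1 and entry to Steps 2 to 5. It is unlikely to matter if the drug works as designed, since the expected z is then 3.25. The size rests on the assumed FMI and on a Week 24 ANCOVA standing in for the MMRM; the formula and the simulation agree.

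**What to change.** Change 50 to about 1000 in SAP 8.6.1, 8.6.1.1 and the code in 12.5. The SD of a p-value near 0.05 then falls to about 0.001 (0.0009 to 0.0019 over the assumed FMI range), more than a fourfold cut. The change reaches the first secondary endpoint through the cross-reference in 8.7.1.1, so no separate rule is needed there.

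When the code is finalised before lock, write a numeric seed into items 2 and 4, give item 3 an actual value, and record the sort order of the input data. Report the Monte Carlo error of the primary estimate beside its standard error.

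The cost is SAP wording and computing time. The estimand, the missing-data assumptions and patient numbers do not change.

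### The prototype PROC MI code in SAP 12.5 leaves out baseline ALSFRS-R, which SAP 8.6.1.1 and Tables 5 and 6 require, and item 2 does not show the split by arm

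*SAP*

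**What the plan says.** Protocol 9.4.2 leaves the imputation details to the SAP. SAP 8.6.1.1 supplies them:

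- By arm and in visit order: "For each randomized treatment group, the missing data will be filled sequentially starting at the earliest time point".
- Predictors: "The imputation model will include the following terms: ALSFRS-R total score at previous visits including baseline", together with riluzole and/or edaravone use and "other covariates selected using stepwise regression for the primary analysis". SAP 8.6.1 gives the candidates for that selection as "pre-study disease progression rate, age and baseline percent predicted FVC as model terms".
- Type of model: "based on a multivariate joint normal imputation model".
- Link to the code: "The example SAS code can be found in" Section 12.5.

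Tables 5 and 6 also list earlier scores with baseline, riluzole use and edaravone use wherever they name imputation terms for the sensitivity estimators. They do not list the stepwise-selected covariates.

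SAP 12.5 item 2 opens with "fcs reg(<Week 4 ALSFRS-R total score> = <baseline riluzole use> <baseline edaravone use>". Weeks 8 to 24 add only the preceding post-baseline scores. The VAR list holds the two strata and Weeks 4 to 24. There is no BY or WHERE statement and no treatment variable, although the item's heading says the imputation is done inside each arm. Values are rounded to integers and bounded at 0 and 48. Item 4 (tipping point) repeats the same regressions. Item 3 (placebo-based) is an MCMC example whose VAR list holds only the Week 4 and Week 8 scores.

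**The concern.** The primary MMRM adjusts for baseline ALSFRS-R and for baseline by visit, yet the printed imputation step never sees baseline. A patient with no Week 4 score is imputed from riluzole and edaravone use alone, so two patients in the same stratum with baseline scores of 44 and 28 would draw Week 4 values from the same distribution. This case can occur: the FAS in SAP 6.5.4 admits patients who have only survival status recorded, so a patient may enter with a baseline but no post-baseline score.

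The first secondary endpoint is also affected, because SAP 8.7.1.1 adopts the method of 8.6.1.1. So are the sensitivity analyses that would be programmed from items 3 and 4.

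The missing BY statement is a separate risk. If item 2 were run on a data set holding both arms, imputed scores would be pulled toward a common mean and the treatment difference would shrink. Two programmers, one working from the text and one from the code, would not produce the same primary result.

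**Working it through.** **1. The plan's own figure.** From SAP 4.3.1: difference 1.8, SD 5.5, two-sided alpha 0.05, power 90%, ratio 2:1. Placebo n = (1.960 + 1.282)² × 5.5² × (1 + 1/2) / 1.8² = 10.51 × 30.25 × 1.5 / 3.24 ≈ 147.2, rounded up to 148, so 3 × 148 = 444 in total. The noncentral t power at 444 is 0.900. Allowing 20% loss, 444 / 0.80 = 555. The sample size reproduces, and 1 − 444/555 = 20% is the plan's implied loss. The point does not depend on this; it only sets a plausible missing rate.

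**2. Text against code.**

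| Element | SAP 8.6.1.1 | 12.5 item 2 | 12.5 item 3 (example) | 12.5 item 4 |
|---|---|---|---|---|
| Baseline ALSFRS-R | required | absent | absent | absent |
| Riluzole, edaravone use | required | present | absent | present |
| Selected covariates | required for the primary analysis | absent | absent, as in Tables 5 and 6 | absent, as in Tables 5 and 6 |
| By arm | required | in heading only | placebo data plus active-arm missing data, as intended | active arm selected inside the step |
| Method | joint normal | FCS regressions, rounded, bounded 0–48 | MCMC | FCS regressions, rounded, bounded 0–48 |

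**3. Size, first simulation.** 150 trials, 555 patients 2:1, true effect 1.8, 20% missing at Week 24 under MAR, random-slope data with a Week 24 change SD of about 5.7, 15 imputations, ANCOVA at Week 24.

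- By arm, baseline left out: SE 0.543 → 0.551, and 0.551/0.543 = 1.015, or +1.5%. Paired change in the estimate −0.008 (Monte Carlo SE 0.009).
- Arms pooled, baseline left out: paired change −0.174 (Monte Carlo SE 0.010); mean estimates 1.89 → 1.71.

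**4. Size, second simulation.** 300 runs per row, 555 patients 2:1, true effect 1.8, SD of change 5.5, monotone MCAR dropout, 10 imputations, ANCOVA at Week 24. Assumed, not in the documents: baseline mean 37 and SD 5, placebo change −6, visit error SD 1.2. Entries are mean estimate / mean SE.

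| Missing | Dropouts with no post-baseline score | By arm, with baseline | By arm, no baseline | Pooled, no baseline | Estimate lost by pooled code |
|---|---|---|---|---|---|
| 10% | 0% | 1.795 / 0.504 | 1.790 / 0.502 | 1.724 / 0.501 | 0.071 |
| 10% | 25% | 1.816 / 0.509 | 1.802 / 0.522 | 1.708 / 0.522 | 0.108 |
| 20% | 0% | 1.780 / 0.516 | 1.776 / 0.513 | 1.641 / 0.510 | 0.139 |
| 20% | 25% | 1.723 / 0.525 | 1.723 / 0.550 | 1.531 / 0.547 | 0.192 |
| 30% | 0% | 1.763 / 0.525 | 1.769 / 0.520 | 1.564 / 0.515 | 0.199 |
| 30% | 25% | 1.860 / 0.542 | 1.841 / 0.579 | 1.550 / 0.572 | 0.310 |

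Run by arm, leaving out baseline moves the estimate by at most 0.019. The SE is essentially unchanged when every dropout has a Week 4 score. With a quarter of dropouts lost before Week 4 it rises by 2.6% (0.522/0.509), 4.8% (0.550/0.525) and 6.8% (0.579/0.542) at 10%, 20% and 30% missing. The attenuation comes mostly from pooling: at 20% missing with no early loss, pooled imputation that keeps baseline already gives 1.674 against 1.780.

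**The case against.** SAP 12.5 calls its code a prototype to be finalized before database lock, so the model in 8.6.1.1 can be said to govern. That is fair, and it makes this a correctable inconsistency. But 8.6.1.1 itself sends the programmer to that code, and the baseline omission runs through three items, so it is unlikely to correct itself.

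A reader might infer that the primary analysis will impute both arms together and lose about 9% of the effect (0.174/1.89 in the first simulation). The documents do not support this. The heading of item 2, SAP 6.8.1, SAP 8.6.1.1 and Sensitivity Estimator 2 in Table 5 all specify imputation by arm, and nothing specifies pooling. Item 4 reads an input data set of the same name and selects the active arm inside the step, which suggests that the data set holds both arms. Since the name is generic, that shows ambiguity and no more. The 9% is also measured from a reference of 1.89, about two Monte Carlo standard errors (0.543/√150 = 0.044) above the true 1.8; against 1.8, an estimate of 1.71 is 5% low. Nor is a missing treatment term a fault, since imputation by arm cannot use one.

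A reader might also count the selected covariates as contradicted. They are chosen later, on blinded data, and possibly none will be kept. The MMRM code in item 1 omits them too. Only a placeholder is missing.

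The difference in method is smaller than the labels suggest. Linear regressions of each visit on earlier visits factorize a joint normal model, so the real departures are the rounding and the bounds.

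**Conclusion.** The contradiction over baseline ALSFRS-R stands on the text alone: 8.6.1.1 and Tables 5 and 6 require it, and items 2, 3 and 4 omit it. Item 3 also omits riluzole and edaravone use. With imputation by arm, the consequence is some loss of precision with negligible bias: about 1.5% in the SE in one simulation, and about 5% at the plan's 20% loss if a quarter of dropouts have no post-baseline score. The documents do not give that quarter.

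The absent BY statement in item 2 is an ambiguity to close, because literal use on both arms would attenuate the effect by about 0.07 to 0.31 points at 10% to 30% missing. This would cost effect size and power. It should not be read as the planned analysis.

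All sizes are illustrative. They rest on assumed trajectories and missingness, ANCOVA in place of the planned MMRM, and 10 or 15 imputations in place of 50.

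**What to change.** - Items 2 and 4: add baseline ALSFRS-R to the VAR list and to every imputation regression.
- Item 3: add baseline ALSFRS-R, riluzole use and edaravone use.
- Item 2: add BY treatment, or state that the input data set is already split by arm.
- Item 2: add a placeholder for the stepwise-selected covariates, marked for the primary analysis only. Do not add it to items 3 and 4: the imputation terms in Tables 5 and 6 do not include those covariates, and adding them would create a new conflict.
- Name the same imputation method in 8.6.1.1 and 12.5, and say in the text whether imputed scores are rounded and bounded at 0 and 48.

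The cost is a few lines of prototype code and one sentence of text, made when the programs are finalized before database lock. Data collection, sample size and the testing sequence are unaffected.
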